9.5.2.2 Description of Procedures/Assessments Schedule

9.5.2.3 Total Volume of Blood Sampling

HV COHORT

Table 7 presents the number of blood samples and the total volume of blood that will be collected throughout the study for the HV Cohort. Additional samples may be taken at the discretion of the investigator if the results of any tests fall outside reference ranges or clinical symptoms necessitate testing to ensure subject safety.

Table 7 Summary of Blood Sample Volumes (HV Cohort)

	Sample Volume per Collection (mL)	Number of Collection Time Points	Total Volume Collected (mL)
Clinical laboratory tests	12	Screening: 1 Follow-Up: 1	12×2=24
Viral test	6	Screening: 1	6×1=6
PK blood sampling	4	5	4×5=20
Total			50

OSA COHORT

Table 8 present the number of blood samples and the total volume of blood that will be collected throughout the study for the OSA Cohort. Additional samples may be taken at the discretion of the investigator if the results of any tests fall outside reference ranges or clinical symptoms necessitate testing to ensure subject safety.

Table 8 Summary of Blood Sample Volumes (OSA Cohort)

	Sample Volume per Collection (mL)	Number of Collection Time Points	Total Volume Collected (mL)
Clinical laboratory tests	12	Screening: 1 Follow-Up: 1	12×2=24
Viral test	6	Screening: 1	6×1=6
PK blood sampling	4	7	4×7=28
Total			58

9.5.3 Appropriateness of Measurements

All clinical assessments are standard measurements commonly used in studies of respiratory safety and in particular, Mild Obstructive Sleep Apnea.

The safety assessments to be performed in this study, including hematology analyses, blood chemistry tests, urinalysis, ECG, and assessment of AEs, are standard evaluations to ensure subject safety.

9.5.4 Reporting of Serious Adverse Events, Pregnancy, and Events Associated with Special Situations

9.5.4.1 Reporting of Serious Adverse Events

All SERIOUS ADVERSE EVENTS, regardless of their relationship to study treatment, must be reported on a completed SAE form by email or fax as soon as possible but no later than 24 hours from the date the investigator becomes aware of the event.

Serious adverse events, regardless of causality assessment, must be collected through the last visit and for 28 days after the subject's last dose. All SAEs must be followed to resolution or, if resolution is unlikely, to stabilization. Any SAE judged by the investigator to be related to the study treatment or any protocol-required procedure should be reported to the sponsor regardless of the length of time that has passed since study completion.

The detailed contact information for reporting of SAEs is provided in the Investigator Study File.

For urgent safety issues call: PPD (24/7 number).

For urgent safety issues, please ensure all appropriate medical care is administered to the subject and contact the appropriate study team member listed in the Investigator Study File.

It is very important that the SAE report form be filled out as completely as possible at the time of the initial report. This includes the investigator's assessment of causality.

Any follow-up information received on SAEs should be forwarded within 24 hours of its receipt. If the follow-up information changes the investigator's assessment of causality, this should also be noted on the follow-up SAE form.

Preliminary SAE reports should be followed as soon as possible by detailed descriptions including copies of hospital case reports, autopsy reports, and other documents requested by the sponsor.

The investigator must notify his/her IRB of the occurrence of the SAE, in writing, if required by their institution. A copy of this communication must be forwarded to the Sponsor to be filed in the sponsor's Trial Master File.

9.5.4.2 Reporting of Pregnancy and Exposure to Study Drug Through Breastfeeding

Any pregnancy in which the estimated date of conception is either before the last visit or within 28 days of last study treatment or any exposure to study drug through breastfeeding during study treatment or within 28 days of last study treatment must be reported.

If an adverse outcome of a pregnancy is suspected to be related to study drug exposure, this should be reported regardless of the length of time that has passed since the exposure to study treatment.

A congenital anomaly, death during perinatal period, an induced abortion, or a spontaneous abortion are considered to be an SAE and should be reported in the same time frame and in the same format as all other SAEs (see [Section 9.5.4.1](#)).

Pregnancies or exposure to study drug through breastfeeding must be reported by fax or email as soon as possible but no later than 1 business day from the date the investigator becomes aware of the pregnancy. The contact information for the reporting of pregnancies and exposure to study drug through breastfeeding is provided in the Investigator Study File. The Pregnancy Report Form must be used for reporting. All pregnancies must be followed to outcome. The outcome of the pregnancy must be reported as soon as possible but no later than 1 business day from the date the investigator becomes aware of the outcome.

A subject who becomes pregnant must be withdrawn from the study.

9.5.4.3 Reporting of Events Association with Special Situations

9.5.4.3.1 REPORTING OF ADVERSE EVENTS ASSOCIATED WITH STUDY DRUG OVERDOSE, MISUSE, ABUSE, OR MEDICATION ERROR

Adverse events associated with study drug overdose, misuse, abuse, and medication error refer to AEs associated with uses of the study drug outside of that specified by the protocol. Overdose, misuse, abuse, and medication error are defined as follows:

Overdose	Accidental or intentional use of the study drug in an amount higher than the protocol-defined dose
Misuse	Intentional and inappropriate use of study drug not in accordance with the protocol
Abuse	Sporadic or persistent intentional excessive use of study drug accompanied by harmful physical or psychological effects
Medication error	Any unintentional event that causes or leads to inappropriate study drug use or subject harm while the study drug is in the control of site personnel or the subject.

All AEs associated with overdose, misuse, abuse, or medication error should be captured on the Adverse Event CRF and also reported using the procedures detailed in [Section 9.5.4.1](#) even if the AEs do not meet serious criteria. Abuse is always to be captured as an AE. If the AE associated with an overdose, misuse, abuse, or medication error does not meet serious criteria, it must still be reported using the SAE form and in an expedited manner but should be noted as nonserious on the SAE form and the Adverse Event CRF.

9.5.4.3.2 REPORTING OF STUDY-SPECIFIC EVENTS

Not applicable.

9.5.4.4 Expedited Reporting

The sponsor must inform investigators and regulatory authorities of reportable events, in compliance with applicable regulatory requirements, on an expedited basis (ie, within specific time frames). For this reason, it is imperative that sites provide complete SAE information in the manner described above.

9.5.4.5 Breaking the Blind

In the case of a medical emergency where the appropriate treatment of the subject requires knowledge of the study treatment given, the investigator may break the randomization code for an individual subject. In all such cases, the AE necessitating the emergency blind break will be handled as an SAE in accordance with the procedures indicated above. Any broken code will be clearly justified and documented. The medical monitor must be notified immediately of the blind break.

9.5.4.6 Regulatory Reporting of Adverse Events

Adverse events will be reported by the sponsor or a third party acting on behalf of the sponsor to regulatory authorities in compliance with local and regional law and established guidance. The format of these reports will be dictated by the local and regional requirements.

9.5.5 Completion/Discontinuation of Subjects

The investigator may withdraw the subject from the study at any time for safety or administrative reasons. A subject may elect to discontinue the study at any time for any reason. All subjects who discontinue the study are to complete the study's early discontinuation procedures indicated in the Schedule of Procedures/Assessments ([Table 5](#) and [Table 6](#)).

The investigator will promptly explain to the subject involved that the study will be discontinued for that subject and provide appropriate medical treatment and other necessary measures for the subject. A subject who has ceased to return for visits will be followed up by mail, phone, or other means to gather information such as the reason for failure to return, the

status of treatment compliance, the presence or absence of AEs, and clinical courses of signs and symptoms.

Subjects who discontinue early from the study will be discontinued for 1 of these primary reasons: AE(s), lost to follow-up, subject choice, withdrawal of consent or other. In addition to the primary reason, the subject may indicate 1 or more of secondary reasons for discontinuation. Study disposition information will be collected on the Subject Disposition CRF.

A subject removed from the study for any reason will be replaced.

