9.1.2 Obstructive Sleep Apnea (OSA Cohort)

In the OSA Cohort, this will be a randomized, double-blind, placebo-controlled, 2-period crossover study. Lemborexant will be compared with placebo, using for the primary endpoint the AHI on the last night of dosing (both treatment periods), and with secondary endpoints that assess oxygen saturation as SpO₂. As with the HV cohort, there will be 2 phases, Prerandomization and Randomization. The Prerandomization Phase will last up to 21 days and will consist of the Screening Period and Baseline Period. The Baseline Period will last less than 1 day, and is on the same day as the Treatment Period 1, Study Day 1.

At Baseline, subjects will undergo a screening PSG to confirm the diagnosis and severity of OSA. At specified visits throughout the Prerandomization Phase and the Randomization Phase, all subjects will undergo routine safety and pharmacodynamics assessments. Adult and elderly subjects with mild OSA will be randomized to treatment sequences D or E (see [Table 3](#)) each consisting of 2 Treatment Periods, each of 8 nights' duration, in which subjects will receive lemborexant 10 mg or placebo; the Treatment Periods will be separated by a washout interval of at least 14 days. When the subject is discharged from the clinic after Treatment Period 2, the Follow-Up Period will begin. The Follow-Up Period will have a duration of at least 14 days, during which the subjects will not receive any treatment. At the end of the Follow-Up Period, subjects will return to the clinic for an EOS visit. If subjects discontinue prematurely, they will undergo an Early Termination (ET) Visit and will then be followed for at least 14 days, after which, an EOS visit should be scheduled. A sufficient number of subjects will be randomized to ensure that 20 evaluable adult subjects (<65 years) and 10 evaluable elderly subjects (≥65 years) complete the study. An evaluable subject is defined as having AHI validly calculated from PSG recoding for every Treatment Period.

No interim analysis is planned.

The EOS will be the date of the last study visit for the last subject.

An overview of the study design for the HV cohort and OSA cohort is presented in [Figure 1](#) and [Figure 2](#), respectively.

[figure not shown]

Figure 1 Study Design for HV Cohort

EOS = End of Study, ET = Early Termination Visit, S = Sleep Laboratory, R = randomization.

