9.3 Selection of Study Population

For the HV Cohort, a sufficient number of subjects will be screened in order to ensure that a total of 12 evaluable subjects complete the study ((8 evaluable adult subjects [<65 years] and 4 evaluable elderly subjects [≥ 65 years])). Discontinued subjects may be replaced to ensure 12 subjects complete all 3 Treatment Periods.

For the OSA Cohort, a sufficient number of subjects will be screened in order to ensure that a total of 30 evaluable subjects complete the study (20 evaluable adult subjects [<65 years] and 10 evaluable elderly subjects [≥ 65 years])). Discontinued subjects may be replaced to ensure 20 adults and 10 elderly subjects complete both Treatment Periods.

Subjects who do not meet all of the inclusion criteria or who meet any of the exclusion criteria will not be eligible to receive study drug.

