5.2 Study Subjects

5.2.1 Definitions of Analysis Sets

Analyses defined below are for each cohort separately.

Safety Analysis Set: Group of subjects who received study drug and have at least one postdose safety assessment.

Pharmacodynamic Analysis Set: The PD Analysis Set is the group of subjects who received at least 1 dose of study drug in each Treatment Period and who had sufficient PD data to derive at least 1 primary PD parameter.

Pharmacokinetic Analysis Set: Group of subjects who received at least 1 dose of lemborexant and who had sufficient PK data to derive at least 1 PK parameter.

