5.3.5 Handling of Missing Data, Dropouts, and Outliers

In general, missing values due to subject discontinuation, missed or unusable assessments will not be imputed.

Incomplete/Missing data will not be imputed, unless otherwise specified; i.e., all missing values will remain as missing in all statistical analyses and listings, unless otherwise specified.

Outliers: No formal statistical analyses will be performed to detect and/or remedy the presence of statistical outliers.

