5.4.1 Primary Pharmacodynamic Analyses

Analysis for the Primary Endpoint

HV Cohort: Mean SpO₂ during TST will be analyzed using a mixed effect model. The model will include fixed effects for sequence, period, and treatment, and a random effect for subject within sequence. The following will be presented: least squares (LS) means, difference in LS mean of lemborexant 10 mg and lemborexant 25 mg compared to placebo, a two-sided 90% CI (equivalent to a one-sided lower 95% CI) for the true mean difference (lemborexant – placebo) in SpO₂ and *p*-value. If the lower bound of the one-sided 95% CI of the treatment difference of SpO₂ is less than -5, this will provide evidence that the given dose of lemborexant does not result in a clinically significant decrease in SpO₂ compared to placebo.

OSA Cohort: AHI will be analyzed using a mixed effect model. The model will include fixed effects for sequence, period, and treatment, and a random effect for subject within sequence. The following will be presented: LS means, difference in LS mean of lemborexant 10 mg compared to placebo, a two-sided 90% CI (equivalent to a one-sided upper 95% CI) for the true mean difference (lemborexant – placebo) in AHI and *p*-value. If the upper bound of the one-sided 95% CI of the treatment difference of AHI is less than 5, this will provide evidence that the given dose of lemborexant does not result in a clinically significant increase in AHI with mild OSA compared with placebo.

A sensitivity analysis may also be performed on the primary endpoint where outliers are excluded. Other sensitivity analyses may be explored.

Plots of AHI and SpO₂ treatment difference data (both individual and LS Mean) will be used to explore the results.

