8 DEFINITIONS AND CONVENTIONS FOR DATA HANDLING

No missing data will be imputed.

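### Every lemborexant Day 8 AHI in the OSA cohort comes from a subject who stayed on drug to Day 8, and no planned analysis checks whether removals favour the "no increase" conclusion

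*Protocol*

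**What the plan says.** **Replacement.** Protocol 9.5.5: "A subject removed from the study for any reason will be replaced". Protocol 9.3, and the synopsis in the same sense: "Discontinued subjects may be replaced to ensure 20 adults and 10 elderly subjects complete both Treatment Periods". One passage obliges and the other permits.

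**Who counts.** Protocol 9.1.2: "An evaluable subject is defined as having AHI validly calculated from PSG recoding for every Treatment Period". The primary analysis uses the PD Analysis Set (SAP 5.2.1), meaning subjects who "received at least 1 dose of study drug in each Treatment Period and who had sufficient PD data" for at least one primary parameter.

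**Removal tied to respiration.** The synopsis and Protocol 9.1.2.2.1 require an OSA subject to stop if a desaturation criterion is met on the first treatment night. Protocol 9.5.5 also lists adverse events among the reasons for discontinuation.

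**Missing data.** SAP 5.3.5: "missing values due to subject discontinuation, missed or unusable assessments will not be imputed". SAP section 8: "No missing data will be imputed". Table 6 of the protocol schedules no PSG in the end-of-study/early-termination column.

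**Conclusion.** SAP 5.4.1 says of an upper bound below 5 that "this will provide evidence that the given dose of lemborexant does not result in a clinically significant increase in AHI". The only sensitivity analysis it names excludes outliers, and that one is optional. None addresses dropout.

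**The concern.** The primary comparison needs a Day 8 AHI on lemborexant, and only subjects still on lemborexant at Day 8 can supply one. If someone is taken off the drug because breathing worsened, the missing value is probably a high one. Its loss lowers the estimated difference (lemborexant minus placebo), which is the passing direction in this non-inferiority test. Refilling to 30 completers restores the planned precision but not the information lost.

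At stake is the wording of a safety conclusion. As written it covers the dose in mild OSA, while the Day 8 data on drug describe subjects who remained on it for eight nights.

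**Working it through.** **1. What happens to a removed subject**

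- *Removed in Period 1, on either treatment:* not dosed in Period 2, so outside the PD Analysis Set.
- *Removed from lemborexant in Period 2 (Sequence D):* stays in the set with a placebo Day 8 AHI but has no within-subject difference. A generalized least-squares calculation adding five such subjects to 30 completers (15 per sequence) changes the SE of the treatment difference only from 1.341 to between 1.305 and 1.321, for an assumed between-subject variance of 5 to 30.
- *Appendix 13.2 code as printed:* patient is in the MODEL statement as well as in RANDOM. With patient fixed, one-period subjects add nothing to the treatment contrast.

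**2. The plan's own power figure**

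Inputs from SAP section 4 and 5.4.1: margin 5, true difference 1.5, combined within-subject variance 26.96, 30 completers, one-sided 5%.

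- SE = sqrt(2 × 26.96 / 30) = 1.341
- Noncentral t, 28 df, noncentrality (5 − 1.5) / 1.341 = 2.61: power 81.6%, against 82% stated.

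The figure reproduces as a completer calculation with no dropout allowance. Without replacement, power would be 77.8% with 27 completers and 73.2% with 24, so replacement does protect power.

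**3. Pass rates, completers against all dosed**

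Assumptions not in the documents: a fraction f of subjects is removed on lemborexant, with mean AHI difference D. Completers are set at +1.5. Simulation: 30 completer differences from N(1.5, 2 × 26.96), plus a negative-binomial number of removed subjects from N(D, 2 × 26.96). A trial passes if the upper one-sided 95% t-bound is below 5. Completers pass about 82% throughout.

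| f | all dosed, D = +10 | all dosed, D = +20 |
|---|---|---|
| 4% | 75% | not shown |
| 5% | 72% | 53% |
| 10% | 62% | 29% |
| 20% | 39% | 5% |

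The table gives every removed subject a full lemborexant-minus-placebo difference. Someone removed from lemborexant in Period 1 has no placebo night and cannot supply one. If half of the removals are in Period 1 and contribute nothing, the all-dosed rate is about 78% at f = 5%, D = +10, and about 51% at f = 10%, D = +20.

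**4. False claims when the true mean in all subjects equals the margin**

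Completer mean = (5 − f × D) / (1 − f).

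- D = 5 (removal unrelated to AHI): 5.0, false-claim rate 5%.
- f = 5%, D = +10: (5 − 0.5) / 0.95 = 4.74, rate 7.3%.
- f = 10%, D = +10: (5 − 1) / 0.90 = 4.44, rate 10.7%.
- f = 10%, D = +20: (5 − 2) / 0.90 = 3.33, rate 33.3%.

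**5. How many removals it takes**

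With 30 completers averaging 1.5, k removed subjects bring the overall mean to 5 only if each averages 5 + 30 × 3.5 / k. That is 40 for three removals and 26 for five.

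**The case against.** The strongest reply is that the documents point to few removals. The suvorexant OSA crossover described in Protocol 7.2 had 26 subjects and 25 evaluable, so 1/26 = 3.8% were non-evaluable from any cause. Eight of those 25 had an AHI at least 5 higher on drug at the end of treatment, and they still supplied the data. In the lemborexant driving study (Protocol 7.1.3.1) all 48 healthy volunteers completed. This stands: the lower rows of the table, and D = +20 in particular, have no support in the documents.

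A reader might infer that the primary analysis is restricted to subjects who tolerated lemborexant. SAP 5.2.1 does not say that. It requires dosing in each period, not completion, so a Period 2 dropout keeps the Period 1 value. Removal for any reason also covers placebo periods, administrative reasons and subject choice.

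A reader might also infer that replacement causes the selection. It does not: the same Day 8 values would be missing without it.

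Nor do removals vanish from the report. They appear in disposition by sequence with reasons (SAP 5.2.2), in the Safety Analysis Set, and in the tables of adverse events leading to discontinuation (SAP 5.6.1). None of these enters the primary decision, so the gap in SAP 5.4.1 remains.

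**Conclusion.** The concern holds in a limited form. One removal rule is itself a respiratory outcome, Period 1 removals leave the primary set, Period 2 removals from lemborexant add almost nothing to the contrast, and nothing stands in for the missing Day 8 AHI. Any bias from respiratory removals on drug favours passing, and the stated conclusion carries no qualification.

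The size cannot be fixed from the documents, which give neither a dropout rate nor the AHI of removed subjects. At removal rates near the suvorexant experience, and with D assumed at +10, the gap is about 7 points (82% against 75%) at 4% and about 10 points (82% against 72%) at 5%. It is smaller when some removals fall in Period 1, and absent when removal is unrelated to AHI. The documents do not support a claim that the primary result is invalid. They support a cheap improvement to the plan.

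**What to change.** - Make Protocol 9.3, the synopsis and 9.5.5 agree on whether replacement is required or optional. Replacement can stay.
- Prespecify in SAP 5.4.1 one supportive analysis of all dosed OSA subjects, including replaced ones and not limited to those dosed in each period. Where a subject stopped a treatment before Day 8 for an adverse event or the SpO2 criterion, use the Day 1 AHI on that treatment in place of the missing Day 8 value.
- Fit it with subject as a random effect only. Remove patient from the MODEL statement in Appendix 13.2, or one-period subjects contribute nothing.
- Report removals by the treatment being taken at removal.
- If the supportive upper bound is not below 5, word the primary conclusion as applying to subjects who completed 8 nights. The supportive analysis should not become a co-primary gate, because the objective concerns multiple doses and Day 1 is a single night.

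The cost is protocol and SAP wording plus one model run on data already collected. Day 1 AHI is only a proxy: in the suvorexant study, five of the eight subjects with a Day 8-type worsening showed a similar difference on the first night. Subjects removed in Period 1 will recover little information.
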